4.2 Rationale for dose/regimen and duration of treatment

Ofatumumab dose

The dose regimen for ofatumumab for this study is a *loading dose regimen* of 20 mg at Day 1, Day 7 and Day 14, followed by a monthly *maintenance dose regimen* of 20 mg administered every 4 weeks, starting at week 4.

This dose regimen is consistent with the dose and regimen in the Phase 3 development program of ofatumumab in RMS.

Duration of treatment

Treatment duration within the study will be 96 weeks with the primary endpoint being at 96 weeks.

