2.1.2 Visit Windows

2.1.2.1 Visit windows for treatment epoch

Visit-windows will be used for both efficacy and safety data summaries by visit. Visit windows define a time period "around" the targeted visit date as defined in the evaluation schedule of the clinical study protocol. Visit-windows are non-overlapping, and defined without gaps between consecutive visit windows. The width of visit windows may vary over the course of the study period.

Baseline assessments are defined in Section 2.1.1 and do not require a visit window.

The purpose of visit windows is to analyze data based on the actual study days (rather than "nominal" visits). E.g., if a subject's Month 1 visit is delayed; it is possible that the Month 1 data be re-aligned to visit-window Month 2 and be summarized under Month 2.

- For efficacy analyses all nominal visits (i.e. excluding unscheduled visits) will be mapped into one of the defined visit-windows. Note: for the derivation of disability worsening or improvement all visits (scheduled and unscheduled) need to be considered before the worsening or improvement can be confirmed. Similarly, for No Evidence of Disease Activity (NEDA-3), all visits (scheduled and unscheduled) need to be considered.
- For safety analyses all visits (scheduled and unscheduled) will be mapped to visit windows. Safety data from unscheduled visits may be reported separately if applicable.

It is possible that more than one assessment of a subject fall into a particular visit-window. Section 2.1.2.3 deals with the statistical approaches to handle multiple visits in a given visit window.

Tables displaying summary statistics "by visit" will also use the term visit-window as column header; this is to remind the reviewer that multiple assessments of a participant might be summarized. Below tables provide visit-windows definitions for applicable parameters.

Table 2-3 Visit-windows for EDSS / T25FW / 9HPT

Visit-window	Start day	Target day	End day
Week 24	1	168	252
Week 48	253	336	420
Week 72	421	504	588
Week 96	589	672	762

Table 2-4 MRI

Visit-window	Start day	Target day	End day
Week 24	2	168	252
Week 48	253	336	504
Week 96	505	672	762

Table 2-5 Visit-windows for vital signs*

		 			
Visit-window	Start day	Target day	End day		
Week 4	1	28	98		
Week 24	99	168	252		
Week 48	253	336	420		
Week 72	421	504	588		
Week 96	589	672	762		

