2.14 Other Exploratory analyses

Following exploratory endpoints will be analyzed as part of CSR based on FAS population.

2.14.1 6-month Confirmed Disability Worsening (6mCDW)

A 6-month confirmed disability worsening (6mCDW) is defined as an increase from baseline in EDSS sustained for at least 6 months. This means that after a scheduled or unscheduled visit at which the participant fulfills the disability worsening criterion as defined in Table 2-16, all EDSS assessments (scheduled or unscheduled) need to also fulfill the worsening criteria until the worsening ("the event") can be confirmed at the first scheduled visit that occurs in the absence of (confirmed or unconfirmed) relapse 6 months/166 days after the onset of the worsening, or later.

In the time to event (6mCDW) analysis, time will be calculated as (the date of EDSS assessment at onset of the event – date of first administration of study drug+1) for patients with the events. Censoring occurs in those participants who did not experience an event up to the analysis cutoff date (i.e. end of treatment epoch date), this includes participants who had a "tentative" disability worsening that could not be confirmed due to an early discontinuation or any another reason.

The censoring time is calculated as (the date of last EDSS assessment up to analysis cutoff date – date of first administration of study drug+1). Additional details are provided in footnote of Table 2-16.

Table 2-16 Criterion for disability worsening based on change in EDSS score

Total EDSS at baseline*	"Disability worsening" criterion
0	≥ +1.5
0.5 to 5	≥ +1
≥5.5	≥ +0.5

A 6-month confirmed disability worsening can have an onset at any scheduled or unscheduled visit if the disability worsening criterion is met. A disability worsening event can only be confirmed at a scheduled visit in the absence of (confirmed or unconfirmed) relapse if, over a period of 6 months (≥166 days=6*30-14 [visit window]) time interval, all assessments meet the worsening criterion.

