If a participant dies due to MS (EDSS=10 at any time), it will be considered a confirmed disability worsening regardless of the baseline EDSS or the change in EDSS. The time will be calculated as (date of EDSS assessment at a tentative onset of the event – date of first administration of study drug+1) or (date of death – date of first administration of study drug + 1) if a tentative onset date does not exist. Note: Death for other reasons than MS (i.e. not EDSS=10) will not be considered a disability worsening.

*Baseline EDSS is defined as the last EDSS assessment prior to the first dose of study medication (protocol inclusion criterion is EDSS 0-4 at screening)

For statistical analysis, Kaplan-Meier curves (and/or cumulative incidence plots) will be provided to present the time-dependent cumulative probability of participants reaching 6mCDW. Kaplan-Meier (KM) estimates will be calculated for the study with 95% confidence intervals. Separate Kaplan-Meier curves and estimates will also be calculated with 95% confidence intervals for last prior DMT subgroup (fumarates vs. fingolimod).

2.14.2 6-month Confirmed Cognitive Decline (6mCCD)

A 6-month confirmed cognitive decline (6mCCD) is defined as at least a 4-point worsening on score sustained for at least 6 months. Event rate by time interval (0-12 months, 12-24 months) will be provided to participants reaching 6mCCD. Cumulative event rate will be calculated with 95% confidence intervals.

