2.14.7 Proportion of subjects with No Evidence of Disease Activity (NEDA-3)

NEDA-3 is a composite of three related measures of disease activity: (i) no relapses; (ii) no 6-month confirmed disability worsening (6mCDW); (iii) no MRI activity (new of enlarging T2 lesions or Gd-enhancing lesion).

NEDA-3 will be set to "No" if at least one of the following conditions is met; otherwise NEDA-3 will be set to "Yes".

- 6mCDW event
- Confirmed relapse
- ≥1 Gd-enhancing T1 lesions
- ≥1 new/enlarging T2 lesions
- Discontinued from study drug due to either "death" or "lack of efficacy"

Proportions of subjects after 96 weeks that meet the criteria of NEDA-3 will be summarized descriptively by last prior DMT (fumarates vs. fingolimod), along with 95% CI.

NEDA-3 will also be summarized by year (use Day 365.25 as the cut-off of Year 1 and Year 2), as well as by year and by last prior DMT, along with corresponding 95% CI. In addition, each NEDA-3 components (Gd-enhancing T1 lesions, new and enlarging T2 lesions, MRI lesion activity, confirmed relapses, 6mCDW, discontinued from study drug due to either death or lack of efficacy) will be summarized by year.

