2.14.8 Proportion of subjects without MRI activity

The proportion of subjects free of Gd-enhanced T1 lesions (in this scan) at Week 24, Week 48 and Week 96 will be summarized.

The proportion of subjects free of Gd-enhanced T1 lesion (all post-baseline scan) will be summarized. This analysis should only include subjects with MRI results at Week 24, Week 48 and Week 96.

The proportion of subjects free of new or enlarging T2 lesion (all post-baseline scan) will be summarized. This analysis should only include subjects with MRI results at Week 24, Week 48 and Week 96.

MRI scans conducted while on steroid should be kept in this analysis. Above analyses will be repeated by last prior DMT.

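### The by-year NEDA-3 split at Day 365.25 gives Year 2 fewer scheduled chances to record activity, so Year 2 looks better even if activity is constant

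*SAP*

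**What the plan says.** SAP 2.14.7 sets NEDA-3 to No if a 6mCDW event, a confirmed relapse, a Gd-enhancing lesion, a new or enlarging T2 lesion, or discontinuation for death or lack of efficacy is observed. Otherwise it is Yes. The section then adds: "NEDA-3 will also be summarized by year (use Day 365.25 as the cut-off of Year 1 and Year 2", with 95% confidence intervals, overall and by last prior DMT. The parts are split as well: "In addition, each NEDA-3 components (Gd-enhancing T1 lesions, new and enlarging T2 lesions, MRI lesion activity, confirmed relapses, 6mCDW", and discontinuation for death or lack of efficacy.

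The schedule behind these tables is as follows.

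- **Duration.** Protocol 4.2: "Treatment duration within the study will be 96 weeks with the primary endpoint being at 96 weeks". Week 96 is Day 672, with a 14-day window either side (Protocol Table 8-1).
- **MRI.** Post-baseline scans are at Weeks 24, 48 and 96 (Protocol Table 8-1, SAP 2.14.8).
- **EDSS.** Scheduled post-baseline visits are at Weeks 24, 48, 72 and 96 (Protocol Table 8-1, SAP Table 2-3).
- **6mCDW.** SAP 2.14.1 dates the event at onset, requires at least 166 days of sustained worsening and cuts off at the end of the treatment epoch. "A disability worsening event can only be confirmed at a scheduled visit in the absence of (confirmed or unconfirmed) relapse".
- **T2 lesions.** SAP 2.14.5 counts new or enlarging lesions against the previous scan.

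The visible text of 2.14.7 gives no adjustment for observation time or scan count, no Year 2 denominator and no caveat.

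**The concern.** A proportion free of events depends on how long and how often one looks. Year 1 and Year 2, as defined, differ on both counts, and a subject with no observed event defaults to Yes. The shorter and less closely observed year therefore scores better unless true activity rises enough to offset it.

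A reader of the study report will see two adjacent percentages with confidence intervals and take a higher Year 2 figure as improving control on continued treatment. The intervals express sampling error only and give no hint of the schedule effect. A real improvement may well exist, but this table cannot separate it from the calendar.

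**Working it through.** The documents give no expected NEDA-3 figure, so there is none to reproduce.

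**Step 1: count opportunity on each side of Day 365.25.**

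| | Year 1 | Year 2 |
|---|---|---|
| Days, if follow-up ends at Day 672 | 365 | 672 − 365 = 307 (293 to 321 across the visit window) |
| Scheduled scans | Days 168, 336: two | Day 672: one |
| Scheduled 6mCDW onset visits that can be confirmed | Weeks 24, 48: two | Week 72: one |
| T2 interval covered | 336 days plus the lead from the screening scan (up to 60 days) | 336 days |

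A Week 72 onset can be confirmed only at Week 96. With visit windows that gap runs from 658 − 518 = 140 to 686 − 490 = 196 days, so some Week 72 onsets miss 166 days and have no later treatment-period visit. A Week 96 onset cannot be confirmed.

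**Step 2: each component under constant activity.**

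- Relapse-free = exp(−ARR × days / 365.25). At ARR 0.16 (Protocol 12.8): Year 1 exp(−0.16 × 365 / 365.25) = 85.2%; Year 2 exp(−0.16 × 307 / 365.25) = 87.4%. The difference is 2.2 points (1.5 at ARR 0.10, 2.4 at 0.18).
- Any Gd-positive scan = 1 − (1 − p)^scans, with p assumed and scans independent. At p = 1%: 2.0% against 1.0%. At 5%: 9.8% against 5.0%. At 10%: 19.0% against 10.0%.
- 6mCDW at an assumed 2% per confirmable visit: 1 − 0.98² = 4.0% against 2.0%.
- T2-free at an assumed rate of 0.15 per period, ignoring the screening lead: exp(−0.15) = 86.1% in both years.

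**Step 3: composite with the same inputs.**

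- Components independent: Year 1 = 0.8522 × 0.95² × 0.98² × 0.8607 = 63.58%. Year 2 = 0.8742 × 0.95 × 0.98 × 0.8607 = 70.05%. Difference 6.5 points.
- Every Gd-positive subject also T2-positive, so the Gd factor drops out: Year 1 = 0.8522 × 0.98² × 0.8607 = 70.45%. Year 2 = 0.8742 × 0.98 × 0.8607 = 73.74%. Difference 3.3 points.

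**Step 4: two points the visible text leaves open.**

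- *Efficacy cutoff.* Its definition in SAP 2.1 is not visible. If relapses counted to Day 762, the end of the Week 96 windows, Year 2 would have 762 − 365 = 397 days. Its relapse factor becomes exp(−0.16 × 397 / 365.25) = 0.8404, and the gain falls to 3.8 points (independent) or 0.4 (full overlap).
- *Dating of 6mCDW.* If the by-year table used confirmation dates, the counts would be one in Year 1 (Week 48) and two in Year 2 (Weeks 72, 96). Swapping 0.98² and 0.98 gives gains of 3.8 and 0.4.
- *Both together:* +1.1 points (independent) or −2.4 (full overlap).

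**Step 5: effect of moving the boundary alone.** With 336 days on each side, relapse-free is exp(−0.16 × 336 / 365.25) = 86.3% in both periods. Scans and confirmable visits remain two against one, so 64.39% against 69.16% (4.8 points, independent) or 71.35% against 72.80% (1.5 points, full overlap) remains. With one Gd scan per period and 6mCDW left out, every factor is equal and the difference is zero.

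**The case against.** The strongest reply is that this is a descriptive summary of an exploratory endpoint, with no test between years, and that analyses accounting for opportunity sit elsewhere. Gd lesions are analysed per scan (SAP 2.14.4), T2 lesions are annualised (2.14.5), 6mCDW has Kaplan-Meier estimates (2.14.1), and ARR is also summarised by yearly interval (Protocol 12.4.2). SAP 2.14.8 already gives a like-for-like Gd display: "The proportion of subjects free of Gd-enhanced T1 lesions (in this scan) at Week 24, Week 48 and Week 96 will be summarized". All of this is correct and limits the harm. None of it corrects or qualifies the by-year composite.

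Several stronger readings are tempting and are not supported:

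- *All three imbalances certainly favour Year 2.* Only the scan count is fixed by the visible schedule. The relapse-day count assumes that the cutoff is the end of planned treatment. The 6mCDW count assumes onset dating, which 2.14.1 gives for the time-to-event analysis and 2.14.7 does not restate.
- *Week 72 is the only possible Year 2 onset for 6mCDW.* Unscheduled visits can also start an event, and those at least 166 days before the Week 96 visit can be confirmed. The two-to-one count concerns scheduled visits.
- *Two scans against one doubles all MRI activity.* This applies to Gd lesions. The Week 96 scan captures new or enlarging T2 lesions since Week 48.
- *SAP 2.14.8 shares the flaw.* It reports Gd status scan by scan and does not.
- *The cognitive endpoint shares the flaw.* SAP 2.14.2 says "Event rate by time interval (0-12 months, 12-24 months) will be provided to participants reaching 6mCCD", but the instrument, its schedule and the rate's denominator are not visible, so this cannot be checked.

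A further fair objection concerns remedies. A literal Day 336 cut would push on-window Week 48 scans from Days 337 to 350 into the second period. Dropping Week 24 Gd lesions or Week 48 onsets from the only table would discard observed activity.

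**Conclusion.** The point stands as a bias in how a descriptive table will be read. Under constant activity, with relapses followed to the end of planned treatment and 6mCDW dated at onset, Year 2 NEDA-3 is inflated by about 3 points (full Gd/T2 overlap) to 6.5 points (independence). Only the ARR of 0.16 comes from the documents. The 5% Gd risk per scan, 2% 6mCDW risk per visit and T2 rate of 0.15 per period are assumptions, so the size is illustrative.

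The direction is firmest for the Gd row: at any constant per-scan risk, two scans find more positives than one. For the composite it depends on the cutoff and the dating rule, and it could reverse if both went the other way. A reader might infer that any Year 2 advantage is an artefact, or that the main results are compromised. Neither follows: a true improvement is possible, the 96-week NEDA-3 involves no split by year, and the primary ARR model has a time-in-study offset.

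**What to change.** Amend SAP 2.14.7 before database lock:

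1. Divide the periods at the actual Week 48 visit and its scan, not at Day 365.25 and not at a literal Day 336. State a fallback day for subjects who missed that visit. This agrees with Protocol 12.6, which plans NEDA-3 after 48 and 96 weeks.
2. Keep all observed activity in the main by-year rows.
3. Add matched-opportunity rows: Gd status at the Week 48 and Week 96 scans only, and the by-year composite using those Gd results and leaving out 6mCDW. The alternative is to keep 6mCDW but limit onset to the first 24 weeks of each period. That is less clean, because a Week 72 onset has a single chance of confirmation.
4. State that 6mCDW is assigned to a period by onset date.
5. Footnote the days, scheduled scans and confirmable EDSS visits in each period, and how subjects who left before the second period are counted.

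Leave the 96-week NEDA-3 unchanged. The cost is a short SAP amendment, some extra programming, fewer events in the matched rows and a slightly less favourable Year 2. If nothing else is changed, the footnote in item 5 is the minimum.

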2.14.8 Proportion of subjects without MRI activity

The proportion of subjects free of Gd-enhanced T1 lesions (in this scan) at Week 24, Week 48 and Week 96 will be summarized.

The proportion of subjects free of Gd-enhanced T1 lesion (all post-baseline scan) will be summarized. This analysis should only include subjects with MRI results at Week 24, Week 48 and Week 96.

The proportion of subjects free of new or enlarging T2 lesion (all post-baseline scan) will be summarized. This analysis should only include subjects with MRI results at Week 24, Week 48 and Week 96.

MRI scans conducted while on steroid should be kept in this analysis. Above analyses will be repeated by last prior DMT.

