8.3.4 Magnetic Resonance Imaging (MRI)

All subjects will undergo MRI scanning of the brain according to the schedules in Table 8-1.

MRI scans will be read by the central MRI reading center. Prior to the start of the study, MRI technician from each center will receive an MRI Manual, outlining technical implementation, image quality requirements and MRI administrative procedures.

The site will be asked to program the MRI scanner that is designated for evaluation of the study subjects. Site will be asked to perform and submit a dummy scan (so called "dummy or dry run") to the central MRI reading center to assess the image quality and to evaluate the compatibility of the electronic data carrier. Once the dummy run has been accepted, all the parameter settings for the study specific MRI sequences must remain unchanged for the duration of the study. Finally, if the site is already pre-approved for performing conventional MRI scan sequences by the imaging vendor the dummy or dry run may be skipped.

Each MRI scan performed for the study needs to be previewed by a local neuro radiologist. During the study, the quality of each scan performed will be assessed by the central MRI reading center. The MRI scan should be sent to the central MRI reading center upon completion of each individual scan. As soon as the scan is received by the central MRI reading center, it will be evaluated for quality, completeness and adherence to the protocol. Confirmation of MRI quality or a description of the quality problems, if detected, will be communicated to the site. If a scan is incomplete or incorrectly performed, the study center will be asked to repeat it as soon as possible. After completion of the quality check, all scans will be analyzed according to the MRI protocol.

Restrictions to MRI schedule

To avoid interferences caused by steroids (in regards to Gd+ enhancing lesions) for the treatment of MS relapse, the following restrictions apply for this study:

- In case of relapse, if an MRI has been scheduled within 14 days of the initiation of steroid treatment, MRI (with Gd+ enhancement) should be performed before steroid treatment is initiated.
- No MRI (with Gd+ enhancement) should be performed while a subject is on steroid therapy for relapse and within the following 14 days upon termination of steroid treatment.

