2.14.4 Number of T1 Gd-enhancing lesions per scan

Number of Gd-enhancing lesions will be obtained from each MRI scan per protocol assessment schedule. To estimate the number of Gd-enhancing lesions per scan, below variables will be derived.

- The total number of Gd-enhancing lesions will be derived by taking the sum of numbers of Gd-enhancing lesions from all scheduled MRI scans. MRI scans taken within 14 days after the termination of steroid therapy will not be included in analysis of Gd lesion related endpoint.
- The number of MRI scans will be derived by counting the number of scheduled MRI scans with non-missing values for the number of Gd-enhancing lesions.

The mean number of T1 Gd-enhancing lesions per scan and corresponding 95% CI will be estimated using a negative binomial model with log-link with number of relapses in previous year, baseline EDSS, baseline number of T1 Gd-enhancing lesions, the participant's age at baseline and prior MS therapies (fumarates and Fingolimod) as covariates. In addition, separate estimates of T1 lesions and corresponding 95% CIs for last prior DMT (fumarates and fingolimod) and for last prior DMT and duration of washout will be given. In case model has convergence issues, covariates will be dropped with the following order: 1) Number of relapses in previous year; 2) Baseline EDSS; 3) Age. Time-based and subject-based T1 Gd-enhancing lesions will also be summarized.

The reduction rate of mean number of T1 Gd-enhancing lesions per scan over time vs baseline will be estimated using a Generalized Estimating Equation (GEE) for a negative binomial model with log-link and natural log the number of MRI-scans with evaluable Gd-enhancing lesions at each visit as an offset variable, and with number of relapses in previous year, baseline EDSS, the patient's age at baseline and prior MS therapies as covariates. In this analysis, outcome will also include number of T1 Gd-enhancing lesions at baseline, the reduction rate vs baseline will be derived using contrast. The negative binomial model will also be performed by prior MS therapy subgroups. In this analysis, separate models will be implemented for each subgroupDetails of negative binomial GEE models and SAS codes are given in Section 5.4.3.

2.14.5 Number of new or enlarging T2 lesions on MRI per year (annualized T2 lesion rate)

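### The SAP excludes Gd scans in the 14 days after steroids but not scans taken on steroids, and keeps on-steroid scans in the Gd-free proportions

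*SAP*

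**What the plan says.** Protocol 8.3.4 gives its reason first: "To avoid interferences caused by steroids (in regards to Gd+ enhancing lesions) for the treatment of MS relapse". It then sets the restriction: "No MRI (with Gd+ enhancement) should be performed while a subject is on steroid therapy for relapse and within the following 14 days" once treatment has ended. Both periods are covered. T2 lesions are not named in the reason.

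SAP 2.14.4 (Gd lesions per scan) carries over only the second period: "MRI scans taken within 14 days after the termination of steroid therapy will not be included in analysis of Gd lesion related endpoint". Its scan count adds no further condition: "The number of MRI scans will be derived by counting the number of scheduled MRI scans with non-missing values for the number of Gd-enhancing lesions".

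SAP 2.14.8 lists two Gd results, "The proportion of subjects free of Gd-enhanced T1 lesions (in this scan) at Week 24, Week 48 and Week 96 will be summarized" and "The proportion of subjects free of Gd-enhanced T1 lesion (all post-baseline scan) will be summarized", and then one T2 result. Its closing paragraph states "MRI scans conducted while on steroid should be kept in this analysis", with no reason given and no split between Gd and T2.

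SAP 2.14.7 (NEDA-3) uses "≥1 Gd-enhancing T1 lesions" as one component and states no steroid rule.

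**The concern.** The protocol treats a Gd scan taken on steroids as unreliable, because enhancement may be missing when disease is active. The SAP removes the scans from the fortnight after the course but leaves in those from the course itself. In 2.14.4 this happens by omission; in 2.14.8 it is explicit. A lesion-free scan on steroids, from a subject who has just been treated for a relapse, then counts as a true zero in lesions per scan and as Gd-free in the proportions.

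On the protocol's own premise, keeping such a scan tends to understate Gd activity, and a single-arm trial has no control group to absorb the error. The report would also show two Gd results built on different steroid rules without explanation. The same results are repeated by last prior DMT, where each scan carries more weight.

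**Working it through.** **Text comparison**

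| Place | Scan during steroids | Scan in the 14 days after |
|---|---|---|
| Protocol 8.3.4 (Gd) | not to be done | not to be done |
| SAP 2.14.4 | not mentioned; counted if the Gd value is non-missing | excluded |
| SAP 2.14.8, two Gd-free proportions | kept | not stated in this section |
| SAP 2.14.8, T2-free proportion | kept | not stated in this section |
| SAP 2.14.7, Gd component | no rule stated | no rule stated in this section |

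The exclusion in 2.14.4 can be read narrowly (that analysis only) or widely (every Gd endpoint). On the narrow reading, 2.14.8 keeps scans from both periods. On the wide reading, it drops the tail and keeps the course. The conflict with the protocol over on-steroid scans exists either way.

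**Scale**

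The documents give no count of affected scans, so there is no figure to reproduce. This is an illustration.

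Inputs:
- 555 subjects (Protocol 3, SAP 1.1)
- 3 post-baseline scans, at Weeks 24, 48 and 96 (Protocol Table 8-1), so 555 × 3 = 1,665 scans
- relapse rate 0.16 per year (Protocol 12.8, SAP 3)
- steroid course of 3 to 5 days (Protocol 6.2.3)
- tail of 14 days (Protocol 8.3.4)

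Assumptions: every relapse is steroid-treated, scan dates are independent of relapse dates, nobody drops out, and no scan is moved.

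Expected scans in a window of d days = 1,665 × 0.16 × d / 365.25
- during a 3-day course: 266.4 × 3 / 365.25 = 2.2 (0.13% of scans)
- during a 5-day course: 266.4 × 5 / 365.25 = 3.6 (0.22%)
- 14-day tail: 266.4 × 14 / 365.25 = 10.2 (0.61%)

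Largest shift in the all-scan Gd-free proportion, if each affected scan belongs to a different subject and changes that subject's result:
- on-steroid scans only: 2.19 / 555 = 0.39 points to 3.65 / 555 = 0.66 points
- both periods: 12.40 / 555 = 2.2 points to 13.86 / 555 = 2.5 points

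If the affected subjects are removed instead, the proportion moves by at most k/(555 − k), where k is the number removed. For on-steroid scans this is 2.19 / 552.81 = 0.40 to 3.65 / 551.35 = 0.66 points. The sign depends on whether those subjects were Gd-free.

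Over an assumed range of 0.10 to 0.30 relapses per year (the upper end allows for unconfirmed relapses treated with steroids), the counts are 1.4 to 6.8 scans on steroids and 6.4 to 19.1 in the tail.

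**The case against.** The strongest case against is that this hardly matters and that keeping the scans may be deliberate.

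- **Rarity.** Protocol 8.3.4 asks that a scan due within 14 days of starting steroids be done before they start, and it lets the MRI schedule move. On-steroid scans should therefore arise mainly from deviations. This stands, and it makes the counts above too high unless scanning is prompted by relapse. But the SAP writes rules for these scans in two sections, so those rules should agree.
- **Keeping scans protects the analysis set.** The all-scan proportions in 2.14.8 require results at all three visits. Excluding one scan can remove a recently relapsed subject, possibly one with a Gd lesion at another visit, and so raise the Gd-free proportion. This stands. A reader might infer that every error here favours the drug; the documents do not support that for the all-scan analysis. The SAP, however, does not give this reason for its keep rule.
- **The keep rule may have been meant for T2 alone.** It directly follows the T2 proportion. But it is a separate paragraph closing a section with two Gd results, and the next sentence plainly refers to all of them.
- **Text that cannot be seen.** SAP 2.1 breaks off and the content of 5.5 is not shown, so an on-steroid exclusion could sit there. That might complete 2.14.4. It would not remove the explicit keep rule in 2.14.8.
- **NEDA-3.** A reader might infer that the composite needs the same repair. It does not. NEDA-3 is No only when an event is present and Yes otherwise, so making a lesion-free scan non-evaluable still gives Yes, and a confirmed relapse already gives No.

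**Conclusion.** The inconsistency is real on the visible text: the protocol bars both periods, SAP 2.14.4 excludes one, and SAP 2.14.8 keeps the other in Gd results. The size is small, about 2 to 4 of 1,665 scans and at most about 0.4 to 0.7 points on the all-scan Gd-free proportion, under the stated assumptions and before any rescheduling. The larger figures for both periods (12 to 14 scans, 2.2 to 2.5 points) should not be read as the size of the on-steroid gap, because most of those scans lie in the tail that 2.14.4 already excludes.

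Nothing here reaches the main conclusions. The primary relapse analysis and the secondary safety endpoints do not use post-baseline Gd scans. The baseline Gd count is a covariate in the primary model, but Protocol Table 5-1 excludes subjects given systemic corticosteroids in the 30 days before the screening scan. The case for acting rests on coherence and low cost, not on a large bias.

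**What to change.** - In SAP 2.14.4, extend the exclusion so that it covers scans taken during steroid therapy as well as those within 14 days after it ends.
- Apply that same rule to the two Gd-free proportions in 2.14.8, regardless of what the scan shows. A rule that discards negative scans and keeps positive ones would add a bias of its own.
- Limit the keep rule in 2.14.8 to the T2 proportion, since the protocol's reason concerns Gd enhancement only.
- Report the Gd-free proportions with all scans kept as a supportive analysis, because the net direction of the exclusion is uncertain where all three visits are required.
- Leave the NEDA-3 composite as it is.

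The cost is a short SAP amendment and a flag derived from steroid use for relapse, which Protocol 6.2.3 already requires on the Concomitant Medications eCRF. The price is a few non-evaluable Gd scans and slightly fewer subjects in the all-scan Gd-free analysis.
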